8.7 Follow-up of AEs

All AEs that are still ongoing at the end of the study will be followed up until resolution.

9. DOCUMENTATION OF DATA

9.1 Data collection

The data collection tool for this study will be electronic CRF (eCRFs). Paper CRFs (source worksheets) should be completed for each subject. eCRFs and paper CRFs and will contain study data which are verifiable to the source data (i.e., original recordings, laboratory reports, and subject records). In addition, all source data should be attributable (signed and dated). Only the site Investigator and authorised co-workers are entitled to make entries on the eCRFs and CRFs. Concomitant medications may be entered as they appear in the participant's record or as per local standards (generic or trade names may be entered). It is the responsibility of the site Investigator to ensure that the eCRFs and CRFs are kept up-to-date so that they always contain the latest observations on the subjects enrolled.

Pathology and imaging results outside the normal range will be commented upon by the site Investigator. Other data than those requested by this protocol may be recorded as "additional data" in the comments section of the eCRF/CRF; the clinical significance of any additional data should be described. Subjects' data will be stored in a validated database, developed and maintained by the Imperial College Trials Unit.

9.2 Data monitoring

The site Investigator is responsible for ensuring that the study is monitored appropriately in order to ensure compliance with GCP and local regulatory guidelines. Monitoring will be organised by the Sponsor for all sites. The monitor will check the completeness of medical records, verify the accuracy of entries in the eCRFs/CRFs (source worksheets), and ensure adherence to the protocol and compliance with local regulatory requirements. Please see details in the monitoring plan.

10. STATISTICS AND DATA ANALYSIS

Part 1 - Dose finding phase

The highest tolerated dose of Imatinib will be determined using a Bayesian continual reassessment method. An initial dose/toxicity skeleton was generated based on a one-parameter power model and a prior guess of toxicities based on expert opinion and data from the IMPRES trial (10) - see Figure 6. Patients will be recruited into the trial individually; the first patient will receive the lowest dose of Imatinib (100mg daily). The highest tolerated dose will be reassessed after each patient completes follow-up and recommended as the dose for the subsequent patient. Dose escalation between patients will be conducted in increments, with no patient receiving more than 100mg than the previous patient (within the 100mg-400mg dose range), guided by the previous dose administered using a statistical model and with oversight from an Independent Data Monitoring Committee. A safety stopping rule has also been imposed if the model identifies with 90% certainty that the lowest dose has a higher toxicity than the target toxicity level (TTL) of 20%. The minimum and maximum number of patients to enter Part 1 of the trial will be 6 and 13, respectively. Under these constraints, using simulation studies we have explored the operating characteristics of this trial design. If our prior toxicities hold true -see Figure 6- the trial design will correctly predict a dose within 10% of the TTL 90% of the time. After the 13th patient completes follow-up (or if a stopping rule is triggered or otherwise stopped early as described in section Premature Termination of the Trial) the toxicities and 90% credible intervals will be calculated for each dose level to generate the dose/toxicity quotient based on the data and prior experience from compassionate use. The highest tolerated dose will be recommended as the dose closest to 20% toxicity. We will also report SAE counts and toxicity incidence with or without withdrawal from study.

Extension phase

The objective of Part 1 is to recommend a dose of imatinib for Part 2. While this is based on tolerability at 4 weeks, the inclusion of some patients with implanted CardioMEMSTM Heart Failure system and Fitbit activity monitor devices provides the opportunity to record the effect of imatinib on the pulmonary circulation and exercise capacity. These data can inform a harm-benefit assessment around the highest tolerated dose. To investigate this, 4 additional patients (patients 14 to 17) with an implanted CardioMEMSTM Heart Failure system and a Fitbit activity monitor will be recruited and treated with a dose of imatinib at or below the highest

PIPAH Study Page 38 of 47

tolerated dose suggested by the statistical model from Part 1 to gather further data to inform potential benefit. This approach is in line with recommendations from the independent Trial Steering and Data Monitoring (and Ethics) Committees who continue to provide oversight. Sequential recruitment is not required and enrolment of two or more patients in parallel is permitted in the extension phase.

Part 2 - Efficacy Phase

Treatment efficacy at the pre-determined highest tolerated dose will be assessed using a Simons two stage design. A null hypothesis that the true response rate is 0.10 will be tested against a one-sided alternative. The first stage interim analysis will happen after 13 patients have completed the 24-week treatment. If there are 1 or no responses# the study will be stopped. If there are 2 or more responses the trial will continue and recruit another 21 patients, creating a maximum sample size of 34 patients. After the final patient is recruited the null hypothesis will be rejected if 7 or more responses are observed. This design ensures a type I error rate of 0.042 and a power of 0.8034 when the true response rate is 0.27. The expected sample size under the null hypothesis is 21 and the probability of an early termination is 0.6213.

Primary analysis of the response rate (PVR reduction after 24 weeks) will be done using an Intention-To-Treat approach. We will provide an alternative Bayesian analysis based on the posterior distribution of the treatment effect of the highest tolerated dose of Imatinib. Treatment effects will be estimated through 95% confidence intervals and credible intervals for the Bayesian analysis using the posterior distribution which results from the data collected and different priors (including a non-informative one). Vague, sceptical and enthusiastic priors will also be considered. The secondary outcomes assessed will be analysed in a similar manner when possible. Secondary analysis will include linear regression models adjusted for potential confounders (e.g., genotype, age, and gender). Continuous data will be summarised with means (geometric means for log-transformed data, otherwise arithmetic), medians, standard deviations, inter-quartile range, coefficient of variation. Categorical data will be summarised by counts per level within factors. In case of missing data, the missing data mechanism will be explored and multiple imputation applied as a sensitivity analysis if appropriate.

[figure not shown]

Figure 6 - Skeleton

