By definition, the highest tolerated dose is reached in this trial when there is a 20% probability that a patient will not be able to continue the drug for 5 consecutive days. All patients who are tolerating Imatinib will be asked to continue on their assigned dose to the end of week 24 and their clinical

response will be measured by the change in PVR (measured through a follow-up RHC). Dose adjustments within the range 100mg to 400mg daily are permitted at the discretion of the responsible physician according to clinical need but if a patient is unable to tolerate 100mg daily, they are withdrawn from the study.

The objective of Part 2 is to define the clinical response to Imatinib after 24 weeks treatment with the highest tolerated dose by measuring the change in PVR through a follow-up RHC. Some patients from Part 1 will have continued on the highest tolerated dose to 24 weeks and so be evaluable for additional efficacy at this dose. Part 2 will continue recruitment of additional patients to a total of 34 evaluable patients; all patients in Part 2 will receive the highest tolerated dose (defined in Part 1) for 24 weeks. Patients will be monitored for safety at the end of Weeks 4, 8, 12 and 24, with telephone assessments at the end of Weeks 16, 20, and 28. If a patient becomes intolerant of Imatinib, they will be allowed to continue with a reduced dose or alterative treatment as guided by their NHS specialist physician, but they will be withdrawn from the study. Beyond that point, we will not be collecting new data from those patients. The clinical response of all patients who complete 24 weeks on the highest tolerated dose of Imatinib will be measured by change in PVR from baseline at Week 24. The primary efficacy endpoint is a binary variable: for patients with a baseline PVR >1000 dynes·s·cm⁻⁵, success is defined by an absolute reduction in PVR of ≥300 dynes·s·cm⁻⁵at 24 weeks; for patients with a baseline PVR ≤1000 dynes·s·cm⁻⁵, success is a 30% reduction in PVR at 24 weeks.

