4.3.5 Subject identification and replacement policy

After informed consent is obtained, patients who are screened will be assigned a 7-digit permanent identification number (subject ID) such that all patients from each research site are given consecutive identification numbers in successive order of inclusion. The first 4 digits of the will be the designated research site ID, and the last 3 digits will be assigned at the research study centre (e.g., if the site ID is 4410, the third patient screened at 4410 site, would be given the number of 4410003).

A patient who is screened but fails to proceed into baseline assessment (e.g., because entry criteria were not met or enrolment did not occur within the specified time frame) may be considered for screening again. Rescreening will be permitted by the site Investigator on a case-by-case basis. A new informed consent form will be signed in any case of re-screening. A new subject ID will be assigned to the subject. Patients who are discontinued will be replaced. Each replacement is by a default a new subject, who will be assigned a completely new subject ID.

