11.3 Informed consent

Consent to enter the study must be sought from each participant only after a full explanation has been given, an information leaflet offered and time allowed for consideration. Signed participant consent should be obtained. The right of the participant to refuse to participate without giving reasons must be respected. After the participant has entered the trial the clinician remains free to give alternative treatment to that specified in the protocol at any stage if he/she feels it is in the participant's best interest, but the reasons for doing so should be recorded. In these cases the participants remain within the study for the purposes of follow-up and data analysis. All participants are free to withdraw at any time from the protocol treatment without giving reasons and without prejudicing further treatment.

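### The Intention-To-Treat primary analysis of Part 2 cannot be carried out under the protocol's own counting, withdrawal and replacement rules

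*Protocol*

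**What the plan says.** Section 10 sets a Simon two-stage design. "A null hypothesis that the true response rate is 0.10 will be tested against a one-sided alternative", and the alternative response rate is 0.27. The trial stops with 1 or no responses in 13 patients, and the null is rejected with 7 or more in 34. The stated properties are type I error 0.042, power 0.8034, expected sample size 21 under the null and early-termination probability 0.6213. The same section then says: "Primary analysis of the response rate (PVR reduction after 24 weeks) will be done using an Intention-To-Treat approach".

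The conduct rules describe a different population:

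- Section 10, interim: "The first stage interim analysis will happen after 13 patients have completed the 24-week treatment".
- Section 4.1, response: "The clinical response of all patients who complete 24 weeks on the highest tolerated dose of Imatinib will be measured by change in PVR". The final cohort is described there, and in the Study Summary, as 34 evaluable patients.
- Section 4.1, patients who become intolerant of imatinib or cannot continue the prescribed dose: they are withdrawn, and for the intolerant "Beyond that point, we will not be collecting new data from those patients".
- Section 4.3.5: "Patients who are discontinued will be replaced".
- Study Summary (Treatment): Part 1 patients count if they completed 24 weeks on the chosen dose.

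Other text points the opposite way:

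- The Study Summary and section 10 word 34 as a limit on recruitment.
- Section 6.11 brings the end-of-treatment assessment, which lists right heart catheterisation, forward when imatinib is stopped early.
- Section 4.3.4 schedules a telephone call 4 weeks after discontinuation.
- Section 11.3, on participants given treatment other than the protocol's: "In these cases the participants remain within the study for the purposes of follow-up and data analysis".

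**The concern.** In a single-arm trial tested against a fixed 10% null, the choice of who enters the denominator largely determines the result. Intention-to-treat means that everyone who starts the dose is counted. If patients who cannot stay on the drug are removed and replaced until 13 and then 34 completers exist, the observed rate is a rate among those who tolerated 24 weeks. There is no control arm in which the same selection would operate.

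Withdrawal is foreseeable. Section 1.2 reports more discontinuations on imatinib in the earlier Phase III trial, and Part 1 deliberately selects the dose closest to 20% toxicity at 4 weeks.

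This goes beyond detail that a protocol may leave to its analysis plan. Withdrawal, the end of data collection and replacement are rules that sites act on. Scoring withdrawn patients as non-responders later would not repair the design either. With replacement, the number treated passes 34, and the boundary of 7 no longer belongs to the number of patients analysed.

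**Working it through.** **Inputs.** From section 10: n1 = 13, stop if 1 or fewer responses; n = 34, reject if 7 or more; p0 = 0.10; p1 = 0.27; one-sided. The 24-week withdrawal proportion d is not in the protocol, so d = 5% to 30% is an assumption.

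**Step 1: reproduce the plan.** For a response rate p among the patients counted,

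P(reject) = Σ (x = 2 to 13) Bin(x; 13, p) × P[Bin(21, p) ≥ 7 − x].

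- p = 0.10: P(reject) = 0.0420.
- p = 0.27: P(reject) = 0.8034.
- Early termination at 0.10: P[Bin(13, 0.10) ≤ 1] = 0.6213.
- Expected size: 13 + (1 − 0.6213) × 21 = 20.95.

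All four stated figures are reproduced.

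**Step 2: completers with replacement, when 0.10 is the all-treated rate.** If withdrawn patients are non-responders, all responses fall among completers, so the completer rate is 0.10/(1 − d). The same rule is evaluated at that rate.

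| d | completer rate | P(reject) |
|---|---|---|
| 5% | 0.10/0.95 = 0.105 | 0.053 |
| 10% | 0.10/0.90 = 0.111 | 0.067 |
| 20% | 0.10/0.80 = 0.125 | 0.110 |
| 30% | 0.10/0.70 = 0.143 | 0.181 |

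At d = 20% the probability of stopping at the interim falls from 0.621 to 0.504. If 0.10 is instead a completer rate, the type I error is 0.042 at every d.

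**Step 3: ITT counting, when 0.27 was meant as a completer rate.** The all-treated rate is 0.27 × (1 − d).

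| d | all-treated rate | power |
|---|---|---|
| 5% | 0.27 × 0.95 = 0.257 | 0.757 |
| 10% | 0.27 × 0.90 = 0.243 | 0.702 |
| 20% | 0.27 × 0.80 = 0.216 | 0.573 |
| 30% | 0.27 × 0.70 = 0.189 | 0.425 |

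**Step 4: is replacement compatible with a limit of 34?** Obtaining 34 completers takes about 34/(1 − d) starters: 36, 38, 43 and 49 at the four values of d. Recruiting at most 34 and replacing until 34 complete cannot both hold once anyone withdraws, unless Part 1 completers fill the gap. If all 43 treated patients were analysed at d = 20% with the boundary left at 7, then, ignoring the interim, P[Bin(43, 0.10) ≥ 7] = 0.133, against 0.048 for 34 patients.

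**The case against.** The strongest reply is that the stated error rates are correct: the rule gives 0.042 for any 13 and 34 counted patients who respond at 0.10. The protocol never says whether 0.10 describes completers or all treated patients. This stands. A reader might infer that 0.042 is simply wrong, but the document does not support that. It fails only if 0.10 is the all-treated rate, as the ITT label implies, and withdrawn patients are non-responders.

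A reader might also take the 20% as the expected dropout. It is a 4-week tolerability target, defined by interruption of more than 5 consecutive days for Grade 2 or worse events. Section 4.1 also allows a lower dose to go forward if better tolerated. It is not a 24-week withdrawal rate, so only a range can be shown, and higher rates than those tabulated have no basis in the protocol.

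Nor is it settled that withdrawn patients are lost to follow-up. One sentence in section 4.1 ends new data collection, while sections 4.3.4, 6.11 and 11.3 point the other way. Likewise, the wording of 34 as a recruitment limit argues against unlimited replacement. The defect is an unresolved conflict, and it is not certain that every site would run a completer trial.

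Finally, a reader might infer that added PAH therapy would inflate the response rate by a known amount. Section 5.6.1 requires stability only before entry, and the protocol does not say how a PVR fall after a later change is counted. But section 11.3 is general consent text about alternative treatment, and no figure in the protocol allows this effect to be sized.

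**Conclusion.** The contradiction is real and affects the trial's only confirmatory efficacy decision. The ITT statement cannot be honoured together with completer counting, withdrawal without further data, and replacement.

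The consequence for the error rates is conditional. On the ITT reading of 0.10, with withdrawn patients as non-responders, the type I error lies between 0.053 and 0.181 for assumed withdrawal of 5% to 30%, and is about 0.11 at 20%. If 0.27 was meant for completers and ITT is enforced, power lies between 0.757 and 0.425 over the same range, against the stated 0.8034. If both rates are completer rates and completers are counted, the stated figures hold, but the analysis is then not ITT and should not carry that name. The matter should be settled before the interim.

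**What to change.** For the primary efficacy analysis:

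- Count the first 13 and first 34 patients who start the highest tolerated dose, in enrolment order, without replacement.
- Score as non-responders those who die, withdraw or have no evaluable Week 24 PVR by a method that the protocol permits. That means catheterisation or the implanted monitor. Requiring catheterisation alone would wrongly fail monitored patients, whom section 6.11 exempts from it.
- Hold the interim when the 13th such patient reaches, or would have reached, Week 24.
- State that 0.10 and 0.27 are rates among all treated patients. The stated 0.042 and 0.8034 then apply exactly.
- If Part 1 patients contribute, include all who were assigned that dose, whether or not they completed.
- Report completers as a sensitivity analysis.

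Sections 4.1, 4.3.4, 4.3.5, 6.11 and 11.3 must be reconciled on follow-up and replacement. The protocol should also state how a PVR fall after a change in background PAH therapy is counted. That is a choice of estimand which the ITT label alone does not settle.

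The cost is a wording amendment. The response assumption becomes less favourable, since 0.27 must hold in all treated patients. Dropping replacement saves recruits, but somewhat more Part 2 patients may be needed if Part 1 patients are not counted.

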An interim analysis is planned after 13 patients have completed the 24 week treatment on the highest tolerated dose. If there are 1 or no responses in these patients, the study will be stopped. Otherwise, additional patients will be recruited for a total of 34 evaluable patients. The null hypothesis will be rejected if 7 or more responses are observed in the 34 patient cohort. Blood levels of Imatinib will be measured in each patient at baseline and at the end of Weeks 4 and 24. A trough level (noting the time for last dose) will be measured at the assessment on Week 4 and that on Week 24. Dose-limiting toxicity is defined as discontinuation of treatment for more than 5 consecutive days due to Grade 2 or above Adverse Events defined by the NCI Common Terminology Criteria for Adverse Events (version 5.0, 2017), adapted for this study - see Appendix 2. The criteria have been adapted by removing reference to pulmonary hypertension as an adverse event (since this is the indication for this study).

The most common recognised side effects of Imatinib include:

- Muscle cramps
- Joint pains
- Nausea and vomiting
- Swelling of the ankles and face
- Skin rash
- Loose stools
- Unusual bleeding or bruising
- Fatigue

Leg oedema and weight gain can also indicate deterioration in PAH due to right heart failure, rather than Imatinib toxicity. At the discretion of the study physician, a trial of increased dose of diuretics is permitted to help reduce the oedema and weight gain. If the oedema and weight gain are judged to be due to Imatinib toxicity, the dose of Imatinib may be reduced or the drug stopped and the patient is managed according to best clinical practice.

If a patient is unable to continue with the prescribed dose of Imatinib to 24 weeks, they will be withdrawn from the study. These patients may continue with a lower dose of Imatinib or discontinue the drug under the guidance of their local NHS specialist physician.

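### The primary analysis is labelled Intention-To-Treat, but the protocol supports two different denominators for its 13- and 34-patient boundaries, and the stated 0.042 carries over to the Intention-To-Treat rate under only one of them

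*Protocol*

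**What the plan says.** Section 10 tests Part 2 with a Simon two-stage design: "A null hypothesis that the true response rate is 0.10 will be tested against a one-sided alternative". The trial stops with 0 or 1 response in 13 patients and rejects the null with 7 or more in 34. It adds: "This design ensures a type I error rate of 0.042 and a power of 0.8034 when the true response rate is 0.27". Early termination under the null is given as 0.6213 and expected size as 21. On the analysis population it says: "Primary analysis of the response rate (PVR reduction after 24 weeks) will be done using an Intention-To-Treat approach".

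Text that builds a completer denominator:

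- Section 10: "The first stage interim analysis will happen after 13 patients have completed the 24-week treatment". The Study Summary (Treatment) and Section 4.1 add that this is on the highest tolerated dose.
- The Study Summary and Section 4.1 set the final total as 34 evaluable patients. The Study Summary makes a Part 1 patient evaluable only after 24 completed weeks at that dose.
- Section 4.1: "The clinical response of all patients who complete 24 weeks on the highest tolerated dose of Imatinib will be measured by change in PVR".
- Section 4.1: "If a patient is unable to continue with the prescribed dose of Imatinib to 24 weeks, they will be withdrawn from the study". For patients who become intolerant in Part 2, it also ends data collection at withdrawal.
- Section 4.3.5: "Patients who are discontinued will be replaced". No reason for discontinuation is excepted.

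Text that points the other way:

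- The Study Summary limits Part 2 to 34 recruited patients. Section 10 recruits 21 more after the interim, to a maximum of 34. Neither leaves room for replacements.
- Section 6.11 brings the end-of-treatment assessment, which includes right heart catheterisation, forward when imatinib stops early.
- Section 11.3, on patients given alternative treatment: "In these cases the participants remain within the study for the purposes of follow-up and data analysis".

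The protocol does not say how a patient without a 24-week PVR counts in the primary analysis.

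**The concern.** Under an Intention-To-Treat count, a patient who stops for toxicity, worsens or dies stays in the denominator. Under a count of replaced completers, that patient leaves it and another takes the place. The two counts answer different questions: whether the drug works in patients who start it, or in those who can stay on it. The background sections name tolerability as the reason the drug's development has been limited, so the difference is not academic.

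The same boundaries, 1 of 13 and 7 of 34, drive both the interim stop and the final conclusion. Two statisticians working from this protocol could apply them to different patients and reach different decisions. If replacements are recruited and Intention-To-Treat is then applied, more than 34 patients have been treated, and no boundary is given for that number.

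**Working it through.** **Inputs from Section 10.** Stage 1: n1 = 13, stop if 1 or fewer responses. Total n = 34, so stage 2 adds 21. Reject if 7 or more. Null rate 0.10, alternative 0.27.

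**Formulas.** With response probability p:

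- Early termination = (1−p)^13 + 13·p·(1−p)^12
- Rejection = sum over x = 2 to 13 of P[Bin(13, p) = x] × P[Bin(21, p) ≥ 7−x]
- Expected size = 13 + 21 × (1 − early termination)

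**Reproducing the stated figures.** At p = 0.10, early termination is 0.2542 + 0.3672 = 0.6213, expected size is 13 + 21 × 0.3787 = 20.95, and rejection is 0.0420. At p = 0.27, rejection is 0.8034. All agree with Section 10. The calculation is right for 34 patients who each respond with probability p.

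**Reading A: boundaries applied to replaced completers.** Let d be the share not completing 24 weeks. The protocol gives no value, so d is an assumption. Hold the all-treated success rate at 0.10 and count non-completers as failures. The rate among completers is then 0.10/(1−d). Entering it as p:

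| d | Completer rate | Rejection probability | Early termination | Treated to get 34 completers |
|---|---|---|---|---|
| 0 | 0.100 | 0.042 | 0.621 | 34 |
| 5% | 0.105 | 0.053 | 0.596 | 36 |
| 10% | 0.111 | 0.067 | 0.568 | 38 |
| 20% | 0.125 | 0.110 | 0.504 | 43 |
| 30% | 0.143 | 0.181 | 0.427 | 49 |

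The last column is 34/(1−d), rounded up. At d = 20%, 7 responses in 34 completers (20.6%) are 7 in 43 treated (16.3%).

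**Reading B: 13 and 34 are all dosed patients, non-completers kept as failures.** At an all-treated rate of 0.10 the error is 0.042, as stated. If 0.27 was meant as an all-treated rate, power is 0.8034. If it was meant as a completer rate, the all-treated rate is 0.27 × (1−d):

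- d = 10%: 0.243, power 0.70
- d = 20%: 0.216, power 0.57
- d = 30%: 0.189, power 0.42

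**Mixed reading: replace, then count everyone treated.** Scaling both stages by 1/(1−d) gives 15 then 38, 17 then 43, and 19 then 49 patients at d = 10%, 20% and 30%. The protocol sets no boundary for these sizes. Carrying over the counts of 1 and 7 at an all-treated rate of 0.10 gives 0.071, 0.119 and 0.190.

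**The case against.** The best defence is that Section 10 is the governing text. It names Intention-To-Treat, counts stage 2 by recruitment, uses completion only to time the interim, and never says evaluable. The Study Summary caps recruitment at 34. Section 6.11 would give some early stoppers a PVR, and Section 11.3 keeps others for analysis. Section 4.3.5 says discontinued patients are replaced, not that they are excluded from analysis. Handling of missing outcomes is commonly left to a statistical analysis plan, which is not shown.

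Much of this stands: the protocol does not settle on completers. It does not settle on all treated patients either. Withdrawal, replacement and the end of data collection are conduct rules in the protocol, and a later analysis plan cannot recover data that were not collected.

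Stronger readings are tempting but not supported:

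- **That 0.042 is wrong.** It reproduces exactly. It departs from the truth only for an all-treated null, under the completer count, with non-completers as failures.
- **That 20% non-completion is the protocol's own figure.** The 20% target is for treatment interruption over 4 weeks, not study withdrawal over 24. It makes zero non-completion hard to assume but fixes no rate.
- **That multiple imputation would credit responses to patients who stopped.** Section 10 offers it only as a sensitivity analysis, if appropriate.
- **That open-label staff could replace known non-responders.** Without an implanted monitor, Appendix 1 schedules no PVR between baseline and end of treatment.

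**Conclusion.** The contradiction is real and concerns the primary endpoint and both decision boundaries. The protocol names an Intention-To-Treat analysis but contains rules that, if followed, remove patients who stop treatment from the count. Other rules keep them in.

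The size depends on which reading is applied. Under Reading B there is no excess error. Under Reading A, 0.042 belongs to a completer rate of 0.10, and the error for the all-treated rate is about 0.07 to 0.18 over an assumed 10% to 30% non-completion. That range rests on the assumed d and on counting every non-completer as a failure. The excess disappears if nobody stops, or if those who stop are counted and respond as often as completers. Since the figure depends on a choice the protocol leaves open, it must be resolved before the interim analysis.

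**What to change.** In Section 10:

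1. Define the 13 and the 34 as consecutive patients dosed at the selected highest tolerated dose. Include any Part 1 patients who started on that dose, whether or not they completed.
2. Count a patient without a Week 24 PVR, for any reason including death or withdrawal, as not a success at both interim and final.
3. State that replacements do not enter the primary count, and say so in Section 4.3.5 as well.
4. Keep the completer analysis as supportive.
5. State whether 0.10 and 0.27 are rates among all dosed patients.

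Then reconcile the Study Summary and Sections 4.1, 4.3.5, 6.11, 10 and 11.3 with this definition.

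**Cost.** Mainly wording. The error for the all-treated rate is then 0.042 as stated, treating the Part 1 patients as exchangeable with the rest. If 0.27 was meant for completers, power must be restated: about 0.70 at 10% and 0.57 at 20% non-completion.

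The overall cap also needs a check. The Study Summary allows 43 individuals. With 13 in Part 1 and 34 at the selected dose, 13 + 34 = 47, so at least 4 Part 1 patients must count towards the 34. With the 4 extension patients of Section 10, 51 − 43 = 8 must count. Counting only newly recruited Part 2 patients could therefore exceed the cap, so Part 1 patients at the selected dose should be included.
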